## SYNOPSIS OF THE CLINICAL INVESTIGATION PLAN

SPONSOR	Paradigm Spine LLC
NAME OF STUDY PRODUCT	coflex® Interlaminar Technology
Class of Medical Device	Class III
STUDY TITLE	A 2 and 5 year comparative evaluation of clinical outcomes in the treatment of degenerative spinal stenosis with concomitant low back pain by decompression with and without additional stabilization using the coflex® Interlaminar Technology for FDA Real Conditions of Use Study.
INT. PROJECT NUMBER	PAS003
PROJECT MANAGER	TBD
CRO	Musculoskeletal Clinical Regulatory Advisers, LLC CRO Washington, DC
PRINCIPAL INVESTIGATOR and RELATED STUDY SITE	TBD
FURTHER INVESTIGATORS and RELATED STUDY SITES	TBD
RELEVANT LITERATURE	
Stucki, Gerald, MD. et al., Measurement Properties of a Self-Administered Outcome Measure in Lumbar Spinal Stenosis. Spine. Vol. 21(7). pp. 796-803.
 
Pratt RK, MA, FRCS, et al. The Reliability of the Shuttle Walking Test, the Swiss Spinal Stenosis Questionnaire, the Oxford Spinal Stenosis Score and the Oswestry Disability Index in the Assessment of Patients with Lumbar Spinal Stenosis. Spine Vol. 27 (1) pp. 84-91.
 
Fairbank J.C.T., The Oswestry Disability Index, Spine Volume 25, Number 22, pp 2940-2953, 2000^11

DURATION OF THE CLINICAL INVESTIGATION	
Per Patient: 60 months
 
Recruitment 36 months
 
Total: 96 months

OBJECTIVES	Meet FDA mandated post-approval Real Conditions of Use evaluation

METHODOLOGY and STUDY DESIGN	
Prospective, multicenter, concurrently enrolled, propensity score controlled through Month 60.
 
Up to 10 treatment (coflex) sites
 
Up to 10 control (decompression) sites

NUMBER OF PATIENTS	
150 per group (300 total) plus 15% to account for LTF in both; plus 20% in control group and 5% in the study device group to account for trimming of control patients and possible trimming of study device patients during the propensity score design. Therefore, the total enrolled will be 186 coflex patients and 220 decompression control patients.

DIAGNOSIS and INCLUSION CRITERIA	
1. Radiographic confirmation of at least moderate lumbar stenosis, which narrows the central spinal canal at one or two contiguous levels from L1-L5 that require surgical decompression. Moderate stenosis is defined as > 25% reduction of the antero-posterior dimension compared to the next adjacent normal level, with nerve root crowding compared to the normal level, as determined by the investigator on CT Scan or MRI.* The patient may have, but is not required to have for inclusion in the study:
 
(a) Facet hypertrophy and subarticular recess stenosis at the affected level(s);
 
(b) Foraminal stenosis at the affected level(s);
 
(c) Up to stable Grade I degenerative spondylolisthesis (Meyerding classification) or equivalent retrolisthesis as determined by flexion/extension X ray:
 
    i) For single level disease, there may be up to a stable Grade I spondylolisthesis or equivalent retrolisthesis at the affected level as determined on flexion/extension films by the investigator.
 
    ii) For two level disease, there may be up to a stable Grade I spondylolisthesis or equivalent retrolisthesis at only one of the two contiguous affected levels as determined on flexion/extension films by the investigator. Patients with up to stable Grade I spondylolisthesis at two contiguous levels are excluded, but patients with up to Grade I stable spondylolisthesis at one level and equivalent retrolisthesis at the adjacent level may be included.
 
(d) Mild lumbar scoliosis (Cobb angle up to 25°)
 
2. Radiographic confirmation of no angular or translatory instability of the spine (instability as defined by White & Panjabi: Sagittal plane translation >4.5mm or 15% or sagittal plane rotation >15° at L1-L2, L2-L3, and L3-L4;

	
>20° at L4-L5 based on standing flexion/extension X-rays)
 
 
3. VAS back pain score of at least 50 mm on a 100 mm scale.
 
4. Neurogenic claudication as defined by leg/buttocks or groin pain that can be relieved by flexion such as sitting in a chair.
 
5. Patient has undergone at least one epidural injection at any prior time point, AND at least 6 months of prior conservative care without adequate and sustained symptom relief.
 
6. Skeletally mature.
 
7. Oswestry Low Back Pain Disability Questionnaire score of at least 20/50 (40%).
 
8. Appropriate candidate for treatment using posterior surgical approach.
 
9. Psychosocially, mentally, and physically able to fully comply with this protocol, including adhering to scheduled visits, treatment plan, completing forms, and other study procedures.
 
10. Personally signed and dated informed consent document prior to any study-related procedures indicating that the patient has been informed of all pertinent aspects of the trial.
 
 
*The Lumbar Spine (H. Herkowitz ed. 2004, Lippincott Williams, & Wilkins).

EXCLUSION CRITERIA	
 
1. More than two contiguous vertebral levels requiring surgical decompression.
 
2. Prior surgical procedure that resulted in translatory instability of the lumbar spine [as defined by White & Panjabi (see Inclusion Criteria, Item #2)].
 
3. More than one surgical procedure at any combination of lumbar levels.
 
4. Prior fusion, implantation of a total disc replacement, complete laminectomy, or implantation of an interspinous process device at index level.
 
5. Radiographically compromised vertebral bodies at any lumbar level(s) caused by current or past trauma or tumor (e.g., compression fracture).
 
6. Severe facet hypertrophy that requires extensive bone removal which would cause instability.
 
7. Isthmic spondylolisthesis or spondylolysis (pars fracture).
 
8. Degenerative lumbar scoliosis (Cobb angle of greater than 25°).
 

	
 
9. Disc herniation at any lumbar level requiring surgical intervention.
 
10. Osteopenia: A screening questionnaire for osteopenia, SCORE (Simple Calculated Osteoporosis Risk Estimation), will be used to screen patients who require a DEXA bone mineral density measurement. If DEXA is required*, exclusion will be defined as a DEXA bone density measured T score of <math>\leq -1.0</math> (The World Health Organization definition of osteopenia).
 
11. Back or leg pain of unknown etiology.
 
12. Axial back pain only, with no leg, buttock, or groin pain.
 
13. Morbid obesity defined as a body mass index <math>> 40</math>.
 
14. Pregnant or interested in becoming pregnant in the next three years.
 
15. Known allergy to titanium, titanium alloys, or MR contrast agents.
 
16. Active or chronic infection – systemic or local.
 
17. Chronically taking medications or any drug known to potentially interfere with bone/soft tissue healing (e.g., steroids), not including a medrol dose pack.
 
18. History of significant peripheral neuropathy.
 
19. Significant peripheral vascular disease (e.g., with diminished dorsalis pedis or posterior tibial pulses).
 
20. Unremitting back pain in any position.
 
21. Uncontrolled diabetes.
 
22. Known history of Paget's disease, osteomalacia, or any other metabolic bone disease (excluding osteopenia, which is addressed above).
 
23. Cauda equina syndrome, defined as neural compression causing neurogenic bowel (rectal incontinence) or bladder (bladder retention or incontinence) dysfunction.
 
24. Fixed and complete motor, sensory, or reflex deficit.
 
25. Rheumatoid arthritis or other autoimmune diseases.
 
26. Known or documented history of communicable disease, including AIDS, HIV, active Hepatitis
 
27. Active malignancy: a patient with a history of any invasive malignancy (except nonmelanoma skin cancer), unless he/she has been treated with curative intent and there has been no clinical signs or symptoms of the malignancy for at least five years. Patients with a primary bony tumor are excluded as well.
 
28. Prisoner or ward of the state.
 
29. Subject has a history of substance abuse (e.g., recreational drugs, narcotics, or alcohol).
 
30. Subject is currently involved in a study of another investigational product for similar purpose.
 

--	--

	
31. Currently seeking or receiving workman's compensation.
 
32. In active spinal litigation.
 
*Primary location for DEXA scan should be the spine. In the event that the spine T score is in the osteopenic range (-1.0 to -2.5) then a T-Score from the hip may be obtained. If the T-Score from the hip comes back above -1.0 then, at the discretion of the investigator, the patient may be considered for inclusion in the study. Also, a hip DEXA may be used in the event that a spine DEXA cannot be obtained.

INVESTIGATIONAL DEVICE; DOSE and MODE OF APPLICATION	
The coflex® Interlaminar Technology is an FDA approved medical device (P110008) already being marketed in the USA. The coflex® Interlaminar Technology obtained marketing approval in the US on October 17, 2012.
 
The device will be implanted as described in the product brochure (see appendix to this CIP) after surgical decompression in patients with spinal stenosis.

TREATMENT GROUPS	
Group A: decompression surgery without any further stabilization by an implant (control group)
 
Group B: decompression surgery with additional stabilization with the coflex® Interlaminar Technology (treatment group)

OBJECTIVES	
Objective 1: To test the hypothesis that the coflex® device in conjunction with surgical decompression is superior to decompression alone at five years based on Month 60 Clinical Composite Success (CCS).
 
Sensitivity Analysis (Objective 1B): To test the hypothesis that the coflex® device in conjunction with surgical decompression is superior to decompression alone at five years using an alternative definition proposed by FDA to define treatment failures due to epidurals at any time
 
Objective 2: To compare clinical status of patients implanted with the coflex® device in conjunction with surgical decompression relative to surgical decompression alone at two years post operatively by confirming clinical non-inferiority in terms of Month 24 composite clinical success (CCS) defined similarly to the IDE study endpoint.
 
Objective 3: If non-inferiority is shown at two-years, to evaluate evidence supporting superiority at two-years in terms of Month 24 CCS.
 
Objective 4: To evaluate coflex® device performance in a “real conditions of use” study by testing the hypothesis that device performance is not clinically inferior at Month 24 in

	the PAS population relative to device performance defined by IDE study results.
CRITERIA for EVALUATION: 1. EFFECTIVENESS	
Objective 1: Month 60 Composite Clinical Success (CCS)
 
A similar CCS endpoint as was used in the IDE will be used to compare clinical status of patients implanted with the coflex® device relative to surgical decompression at 60 months.
 
Month 60 success for this comparison will require the following items:
 
 
❖ At least a 15 point improvement relative to pretreatment baseline in the Oswestry Disability Index (ODI, range 0-100).
 
❖ No reoperations, revisions, removals, or supplemental fixation at the index level(s);
 
❖ No <math>\geq 2</math> injections or series of injections for any lumbar level**, or nerve block procedures performed to treat spinal stenosis at any lumbar level(s); or a single injection within 12 months of the 5 year endpoint.
 
 
**A series of injections is considered 2-3 injections performed between 24-hour and one week intervals designed to treat a single pain event. Secondary injections performed due to patient demand or recurrence of symptoms following the initial injection are considered separate injections and would constitute a study failure.
 
Additional details, justification, and sensitivity analyses are described in the main protocol text below.
 
Objectives 2 and 3: Month 24 CCS
 
For the comparison to decompression, the Month 24 CCS will be slightly modified to include any surgical intervention at index level(s). This is because the decompression only group receives no device. In summary, when comparing coflex® in conjunction with decompression to decompression alone, Month 24 CCS will require:
 
 
• No “Treatment Failure” on or before the exact 2-year anniversary of the index surgery. Treatment Failure will include: 
 
1. No surgical intervention at the index level
 
2. No lumbar epidural steroid injection including nerve root blocks and facet blocks at any lumbar level
 
 
 
• At least a 15-point improvement relative to pretreatment baseline in the Oswestry Disability Index (ODI, range 0-100).
 
• No major device-related adverse event defined as an event simultaneously both 'Serious' and 'Definitely' on or
 

	
before the exact surgical two-year anniversary. In the decompression alone group, since there is no device, this endpoint will be identified as any serious AE that is classified as definitely related to surgery.
 
Note: The IDE study defined this CCS component as severe and definitely-related. This has been changed to serious and definite for consistency with other spine studies for Objectives 2 and 3 only.
 
Objective 4: Month 24 CCS
 
The identical Month 24 CCS endpoint defined for the IDE study will be used to compare PAS results to IDE study results. These results will be used to update the Bayesian posterior probabilities of non-inferiority and superiority relative to fusion that are summarized in the coflex® SSED.
 
Secondary Criteria:
 
 
• ODI change compared to baseline at 24 and 60 months as a continuous variables and in terms of achieving at least a 15 point improvement.
 
• Change in Visual Analog Scale (VAS) for low back pain (on the 100 mm scale) after 24 and 60 months compared to baseline as a continuous variables and in terms of achieving a 20 point improvement.
 
• Change in leg pain using a Visual Analog Scale (VAS) 100 mm scale after 24 and 60 months compared to baseline as a continuous variable and in terms of achieving a 20 point improvement.
 
• Change in worst leg pain using Visual Analog Scale (VAS) 100 mm scale after 24 and 60 months compared to baseline as a continuous variable and in terms of achieving a 20 point improvement
 
• Change of Zurich Claudication Questionnaire (ZCQ) after 24 and 60 months compared to baseline:               
 
1. Symptom severity (range 1-5)
 
2. Physical function (range 1-4)
 
3. Patient satisfaction (range 1-4, no baseline)
 
4. ZCQ Overall Success (<math>\geq 2</math> of 3 of the following)                   
 
1) Improvement in symptom severity <math>\geq 0.5</math>
 
2) Improvement in physical function <math>\geq 0.5</math>
 
3) Satisfied or somewhat satisfied as defined by a score of <math>\leq 2.5</math> points on the patient satisfaction domain.
 
 
 
5. ZCQ Overall Success components
 
 
 
• Maintenance or improvement in EQ-5D compared to baseline
 

--	---

	
 
• Change from baseline to Month 24 and Month 60 in maximum walking time from treadmill test as a continuous variable and in terms of achieving at least an 8 minute improvement or maximum time of 15 minutes.
 
• Change from baseline to Month 24 and Month 60 in time to symptoms from treadmill test as a continuous variable and in terms of achieving at least an 8 minute improvement or maximum time of 15 minutes.
 
• Neurological status (motor, sensory, reflex, SLR - assessment of maintenance of improvement after surgery throughout study duration).
 
• Radiography Endpoints 
 
1. Assessment of significant migration of the implant or the complete expulsion (significant is defined > 5 mm).
 
2. Assessment of spinous process fracture.
 
3. Assessment of maintenance of foraminal height
 
4. Assessment of adjacent level disease determined by independent radiographic review
 
 
 
• Correlation of foraminal height changes to improvement of walking distance on a treadmill (after 24 and 60 months compared to baseline).
 
• The CCS will be modified to examine the effect narcotics use (opioids and/or opiates) has on treatment success rates. When comparing coflex® in conjunction with decompression to decompression alone, this modified Month 24 CCS will include: 
 
• No “Treatment Failure” on or before the exact 2-year anniversary of the index surgery. Treatment Failure will include: 
 
1. No surgical intervention at the index level
 
2. No lumbar epidural steroid injection including nerve root blocks and facet blocks at any lumbar level
 
 
 
• No persistent new or worsening sensory or motor deficit where persistence is established by identifying new or worsening deficits at Month 18 that do not resolve by Month 24.
 
• No major device-related adverse event defined as an event simultaneously both ‘Serious’ and ‘Definitely’ according to independent Clinical Events Committee (CEC) related to the implant on or before the exact surgical two-year anniversary or exact five-year anniversary. In the decompression alone group, since there is no device, this endpoint will be identified as any serious AE that is classified as definitely related to surgery.
 
 
 

--	--

	
Alternative CCS using treadmill test:
 
An alternative CCS will be assessed as a secondary endpoint for Objectives 1, 2, and 3. For this modified CCS, the criterion that the Oswestry Disability Index (ODI) must improve by at least 15 points will be replaced by a criterion that more directly measures physical function. This endpoint (CCS-WDT) is a function of the maximum time a patient can walk on a treadmill (up to 15 minutes) before symptoms are too severe to continue. The specific treadmill success criterion will be an improvement in the total walking time from baseline to Month 24 of at least 8 minutes. For patients with a baseline value that is >7 minutes, the Month 24 walking test success criteria is the ability to achieve the maximum walking test time of 15 minutes. This allows patients with baseline values >7 min to be able to numerically meet this success criterion.

CRITERIA for EVALUATION: 2. SAFETY	
Documentation of Adverse Events and SAEs and implant related adverse events (e.g., breaking of implants). Specific AEs will be summarized according to incidence (per patient) and counts of AE over time.
 
Assessment of revisions and additional stabilizations.
 
Assessment of epidurals.
 
Assessment of narcotics usage.

STATISTICAL METHODS	
Accounting for non randomized treatment group comparisons. This study design includes concurrently enrolled, but non-randomized investigational and control arms. Covariate balance will be achieved through the use of sub classification based on propensity score (PS) quintiles. The PS subclasses will be determined by an outcomes blinded statistician soon after prospective enrollment is completed and before most if not all patients are evaluable for the two-year effectiveness endpoint. The process of assigning patients to subclasses will be submitted to FDA for review and acceptance prior to unblinding of the PS statistician. Selection into a PS subclass is the observational study equivalent to randomization. Subclasses will be determined using methods designed to insure that within subclass, groups are well balanced with regard to a rich clinically relevant set of baseline covariates. Analyses will proceed as if patients were randomized to treatment group within subclass and effectiveness outcomes will be compared between groups using methods that account for PS subclass. To make use of the beta-binomial updating from prior to posterior it is necessary to have a count of the numbers of successes and failures observed in the prospective trial for both groups. These are added to prior beta distribution parameters that reflect (what amounts to) the prior numbers of success and failures. Combined, these sums of successes and failures determine the Bayesian

posterior distribution. This simplicity owes to the use of a so-called ‘conjugate’ prior distribution. To adjust for PS subclass, the average success rate over the 5 subclasses will be computed for each treatment group. This is to allow each quintile subclass to contribute equally to the estimated success rates. Consequently, covariate balance is preserved in the final estimates of CCS probabilities. Additional details and justification for this approach including missing data strategies are provided below.

**Objective 1: (5-year superiority)** This objective is to test the hypothesis that the coflex® device in conjunction with surgical decompression is superior to decompression alone at five years. This objective will be met by testing the following superiority hypotheses:

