 Stucki G et al., Measurement Properties of a Self-Administered Outcome Measure in Lumbar Spinal Stenosis. Spine. Vol. 21(7). pp. 796-803.

- The CCS will be modified to examine the effect narcotics use (opioids and/or opiates) has on treatment success rates. When comparing coflex® in conjunction with decompression to decompression alone, this modified Month 24 CCS will include:
  - No “Treatment Failure” on or before the exact 2-year anniversary of the index surgery. Treatment Failure will include:
    - No surgical intervention at the index level
    - No lumbar epidural steroid injection including nerve root blocks and facet blocks at any lumbar level
  - No persistent new or worsening sensory or motor deficit where persistence is established by identifying new or worsening deficits at Month 12 that do not resolve by Month 24.
  - No major device-related adverse event defined as an event simultaneously both ‘Serious’ and ‘Definitely’ according to independent Clinical Events Committee (CEC) related to the implant on or before the exact surgical two-year anniversary or exact five-year anniversary. In the decompression alone group, since there is no device, this endpoint will be identified as any serious AE that is classified as definitely related to surgery.
- No use of a narcotic (opioids or opiates) at Month 24.

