## **7.14. Alternative and Incremental Composite Clinical Success**

Secondary analyses may also involve device group comparison on the basis of “alternative and incremental composite clinical success endpoints” in order to provide a richer assessment of the multi-factorial treatment response using the approach recently described by Bae, Lauryssen, Maislin et al (2015). Incremental composite endpoints are constructed by adding additional success criteria. An example of this is the addition of the requirement that there is no Month 24 oral narcotics (opioids and opiates) use. This variable will be evaluated as an outcome variable alone and as part of the incremental CCS analyses.

---

 Kaplan EL and Meier P. Nonparametric estimation from incomplete observations, Journal of the American Statistical Association, 53:457-481, 1959.

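### The narcotics-modified Month 24 CCS is listed without the ODI criterion in all three places, and the synopsis list also lacks the narcotics criterion

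*Combined protocol and SAP*

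**What the plan says.** The synopsis (Secondary Criteria) and Sections 3.3 and 5.2 each announce the endpoint in the same words, "The CCS will be modified to examine the effect narcotics use (opioids and/or opiates) has on treatment success rates", and then set out what "this modified Month 24 CCS will include". All three lists contain no Treatment Failure (index-level surgery or lumbar injection) by two years, no persistent new or worsening neurological deficit, and no major device-related adverse event, with a substitute rule for the control arm. Sections 3.3 and 5.2 add "No use of a narcotic (opioids or opiates) at Month 24". The synopsis list stops before that item, and the text moves on to the treadmill-based CCS.

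The base Month 24 CCS for Objectives 2 and 3 is listed in the synopsis, Section 3.1 and Section 5.1. Each listing has an ODI requirement: "At least a 15 point improvement relative to pretreatment baseline in the Oswestry Disability Index (ODI, range 0-100"), apart from a hyphen in the synopsis.

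Section 7.14 explains the construction in general terms: "Incremental composite endpoints are constructed by adding additional success criteria". It continues: "An example of this is the addition of the requirement that there is no Month 24 oral narcotics (opioids and opiates) use".

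**The concern.** An incremental composite keeps every base criterion and adds one, so its successes must be a subset of the base successes. The fall in the success rate then shows what the added criterion costs in each arm. The listed endpoint lacks that property because the ODI criterion has gone.

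Programmed from Section 3.3 or 5.2, the modified CCS differs from the base CCS by two changes at once, and the comparison cannot be attributed to narcotics. Programmed from the synopsis, success does not depend on narcotics use at all. If the text stays as it is, whether ODI belongs in the endpoint may be settled only when outcomes are in view.

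**Working it through.** The plan has no figure to reproduce. The check is a comparison of components.

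| Item | Base: synopsis | Base: 3.1 | Base: 5.1 | Modified: synopsis | Modified: 3.3 | Modified: 5.2 |
|---|---|---|---|---|---|---|
| No Treatment Failure by two years | yes | yes | yes | yes | yes | yes |
| ODI improvement of at least 15 | yes | yes | yes | **no** | **no** | **no** |
| No persistent neurological deficit | no | no | yes, from Month 12 | yes, from Month 18 | yes, from Month 12 | yes, from Month 12 |
| No major device-related event | yes | yes | yes | yes | yes | yes |
| Event item mentions five years | no | yes | no | yes | yes | yes |
| No narcotic at Month 24 | not applicable | not applicable | not applicable | **no** | yes | yes |

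The consequence can be written out without rates. Let F be meeting all the listed items other than ODI and narcotics, A the ODI response, and N no narcotic at Month 24. Take the base CCS as in Section 5.1, which carries the neurological item, and ignore the Month 12 versus Month 18 difference.

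- Base CCS: P(F and A).
- Additive endpoint on the Section 7.14 principle: P(F and A and N).
- Section 3.3 and 5.2 lists: P(F and N) = P(F and A and N) + P(F and not A and N).
- Synopsis list: P(F) = P(F and A) + P(F and not A).

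Three things follow.

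1. The Section 3.3 and 5.2 lists exceed the additive endpoint by P(F and not A and N). These are patients free of the listed failures and of narcotics, but without the ODI gain. The term lies between 0 and P(F and not A).
2. The Section 3.3 and 5.2 lists minus the base CCS equal P(F and not A and N) − P(F and A and not N). The sign is open: it depends on whether narcotic-free ODI non-responders outnumber narcotic-using ODI responders.
3. The synopsis list minus this base CCS equals P(F and not A), which cannot be negative, and N does not appear. Against the synopsis's own base list, which has no neurological item, that sign is open too.

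The between-arm difference shifts by the arm difference in the extra term, in a direction the documents do not determine.

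The treadmill CCS provides a contrast. When the plan means to take ODI out, it says so: "the criterion that the Oswestry Disability Index (ODI) must improve by at least 15 points will be replaced by a criterion", repeated in Section 7.8. Nothing similar is said for the narcotics CCS.

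**The case against.** Four arguments run the other way.

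- **The lists need not be exhaustive.** They say what the modified CCS will include, whereas the base listings say what it will require, and nothing states that ODI is dropped. An analyst could carry ODI over. This makes a drafting omission the likely explanation, but it does not settle the definition. The lists restate other unchanged components in full, down to the control-arm rule, so a programmer would reasonably take them as complete.
- **Section 7.14 already gives the additive construction.** It states a principle and offers narcotics as an example. It lists no components and does not refer to Section 3.3. A reader might infer that it formally defines this endpoint and that the lists contradict it outright. The text does not go that far: the section says such analyses may be done, and its heading also covers alternative composites, which need not be subsets of the base CCS. Equally, it is too general to override three explicit lists.
- **An item may have been lost in layout.** That could account for one closing bullet in the synopsis, but not for ODI missing from three separate lists.
- **Little depends on it.** This stands. The endpoint is secondary, Section 7.9 reports such endpoints with counts, percentages and intervals, and no decision threshold is attached. ODI response is a separate secondary endpoint, and Section 7.14 also evaluates narcotics use alone. The intended composite can be rebuilt from patient data, so it would be too strong to say that the narcotics question becomes unanswerable.

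**Conclusion.** The point holds as a definition that is wrong as written, for a secondary and descriptively reported endpoint. The ODI criterion is missing from all three lists, and the narcotics criterion is missing from the synopsis list. The listed endpoint is not additive, and its difference from the base CCS would not isolate narcotics use. No primary objective, prior, sample size, power or type 1 error figure is touched.

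The size cannot be given, because the documents contain no component rates for ODI response or narcotic use. A reader might infer that the modified rate must come out above the unmodified CCS. The documents do not support that for the Section 3.3 and 5.2 lists, where the sign depends on unknown rates. For the synopsis list it follows only if the base CCS carries the same neurological item.

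The conclusion rests on two readings: that the lists are meant as definitions, and that the narcotics line in Sections 3.3 and 5.2 belongs to the modified CCS rather than standing as a separate endpoint.

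**What to change.** In the synopsis, Section 3.3 and Section 5.2, replace the three lists with one definition by reference: *the Month 24 CCS of Objectives 2 and 3, including its ODI improvement of at least 15 points, and in addition no narcotic use (opioid or opiate) at Month 24*. If ODI is meant to be dropped, say so, as for the treadmill CCS, and do not present the endpoint as incremental.

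Inserting the missing lines alone would not make the lists agree with the base CCS. The same edit should reconcile:

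- the neurological item, which is in the Section 5.1 base CCS but not in the synopsis or Section 3.1 base lists;
- the start of persistence. The synopsis has "identifying new or worsening deficits at Month 18 that do not resolve by Month 24", and Section 5.2.5 also uses Month 18, while Sections 3.3, 5.1 and 5.2 use Month 12. The visit schedule in Section 4.8.10 has no Month 18 visit;
- the reference to an exact five-year anniversary inside a Month 24 endpoint;
- oral narcotics in Section 7.14 against any narcotic in Sections 3.3 and 5.2.

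The cost is a wording amendment in those sections. ODI is collected at Month 24 (Sections 4.8.5 and 4.8.10), and the type of painkiller is captured through Visit 5, the Month 24 visit (Section 4.7.8). Section 4.7.8 names drug classes and not route, so an oral-only version would need a check that route is recorded. The definition should be fixed before Month 24 outcomes are unblinded.
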